Our secondary aim is to determine whether the intervention affects 1) the frequency of positive-urine tests for opioids and 2) the frequency and proportion of subjects self-reporting opioid use. (We recognize that, due to constraints on in-person follow-up imposed by the COVID-19 pandemic, individuals who are most likely to get urine tests are those who are in treatment and those who might subsequently present to the emergency department (ED) for opioid-related complaints.) Our hypothesis is that our intervention will decrease both. As in the previous aim, data will be collected remotely/electronically from self-report and EPIC. If the sources of information were to conflict, then what is entered in EPIC will take precedence.

Data from our entire cohort will be compared in aggregate with patients who were started on BUP in the ED over the same time period and with historic controls who received only printed resources addressing OUD as reported in [name] et al.¹¹

2. Probable Duration of Project: State the expected duration of the project, including all follow-up and data analysis activities.

The probable duration of the project is 2 years (from 09/2019-09/2021). There is potential for extension after this time, depending on availability of funding.

3. Background: Describe the background information that led to the plan for this project. Provide references to support the expectation of obtaining useful scientific data.

Importance of problem.

The epidemic of opioid use disorder (OUD) prompted a presidential declaration of a public health emergency in October, 2017, and it was extended in January, 2018.² In 2016, an unprecedented 63,632 deaths in the United States (US) were attributed to drug overdose; 2/3 of these involved opioids.³ The deaths due to drug overdose in 2016⁴ exceeded the number of traffic fatalities during the peak year of 1972,⁵ the number of HIV deaths at their peak in 1995, the final year before the introduction of triple antiviral therapy,⁶ and the peak year for gun violence in the US, which was 1993.^{7,8} Nonfatal opioid overdoses are highly associated with ongoing OUD and recurrent overdoses. One study reviewing emergency medical service (EMS) records of

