
- d. For multi-site studies for which the Yale PI serves as the lead investigator: N/A
 - i. How will adverse events and unanticipated problems involving risks to subjects or others be reported, reviewed and managed? N/A
 - ii. What provisions are in place for management of interim results? N/A
 - iii. What will the multi-site process be for protocol modifications? N/A

12. **Statistical Considerations:** Describe the statistical analyses that support the study design.

Study design

Primary outcomes

The primary outcomes will be 1) percentage of individuals with repeat opioid overdose events requiring naloxone resuscitation, identified using YNHH's electronic medical record system (EPIC), and 2) percentage of individuals engaged in any treatment for OUD or who are in remission. Data will be recorded at baseline and at 30 and 180 days after consent to participate in the research.

Secondary outcomes

The secondary outcomes will be 1) frequency and percentage of individuals with positive opioid tests (urine) recorded in their hospital charts or during medication program monitoring, and 2) frequency and percentage of subjects with self-reported opioid use. Data will be recorded at baseline and at 30 and 180 days after consent to participate in the research.

Statistical analyses

We will document demographics (sex, race/ethnicity, age, education, employment status, etc.) and clinical characteristics (e.g., heroin use, non-opioid use in the past 6 months, lifetime treatment for addiction etc.) among all cohorts. χ^2 tests (2 df) will be employed to detect statistically significant differences.

Group	X	No X	Total
PRIDE + CCAR intervention			
BUP-initiated in ED after OD			
Historical control(s)			
Total			

For primary outcomes, "X" is % of repeated overdose events or % of treatment engagement. For secondary outcomes, "X" is frequency or % positive testing for opioid tests or % (self-reported) opioid abuse.

Sample size determination

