Our research is funded by an R01 through the CDC, which no longer issues hardcopy Certificates of Confidentiality (CoCs). However, as noted above, per section 2012 of the 21st Century Cures Act, a CoC "automatically" has been issued by the agency.

<https://www.cdc.gov/od/science/integrity/confidentiality/applinst.htm>

SECTION V: POTENTIAL BENEFITS

Potential Benefits: Identify any benefits that may be reasonably expected to result from the research, either to the subject(s) or to society at large. (Payment of subjects is not considered a benefit in this context of the risk benefit assessment.)

Participants are expected to directly benefit from the educational, counseling, and medical resources and contacts. We expect that this will provide better outcomes in the short- and possibly long-terms.

SECTION VI: RESEARCH ALTERNATIVES AND ECONOMIC CONSIDERATIONS

1. **Alternatives:** What other alternatives are available to the study subjects outside of the research? Participants may decline study participation or participate in another study. BUP can be started in the ED for individuals willing to accept it at the time of an OD. Other resources for harm reduction and treatment are routinely provided at the time of an ED visit, but are seldom associated with positive short-term outcomes.

2. **Payments for Participation (Economic Considerations):** Describe any payments that will be made to subjects, the amount and schedule of payments, and the conditions for receiving this compensation.
Participants will receive 3 payments of \$25 (for a total of \$75) after consent and after the first and second meetings. Each payment is given as a \$25 gift card to Stop & Shop. Initial payments may be obtained upon consent in the ED; subsequent payments will be mailed or provided electronically, according to subjects' preferences.
3. **Costs for Participation (Economic Considerations):** Clearly describe the subject's costs associated with participation in the research, and the interventions or procedures of the study that will be provided at no cost to subjects.
The research will not generate any costs to participants, as we expect that study personnel will meet with them at settings and times of participants' choosing and convenience. All medical and laboratory testing is part of participants' routine care and is not directly a feature of the research itself. Additionally, for those electing to receive BUP, grant funding will cover its cost.

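### The urine outcome has no place for people never tested, so cohort differences mix opioid use with how often each cohort is tested, in a direction that depends on the comparator

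*Combined protocol and SAP*

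**What the plan says.** Section I, item 12 (Secondary outcomes) gives the first secondary outcome as "frequency and percentage of individuals with positive opioid tests (urine) recorded in their hospital charts or during medication program monitoring", recorded at baseline and at 30 and 180 days. Under Statistical analyses, an empty table has three rows (intervention, BUP started in the ED, historical controls) and the columns X, No X and Total. For the secondary outcomes, X is "frequency or % positive testing for opioid tests or % (self-reported) opioid abuse". The comparison is by chi-square: "tests (2 df) will be employed to detect statistically significant differences". There is no column or rule for a person without a test.

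Three other places bear on this:

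- Section VI, item 3 (Costs for Participation): "All medical and laboratory testing is part of participants' routine care and is not directly a feature of the research itself".
- The secondary aim at the start of Section I, which cites pandemic limits on in-person follow-up: "individuals who are most likely to get urine tests are those who are in treatment and those who might subsequently present to the emergency department", in the latter case for opioid-related complaints. The same paragraph hypothesises a decrease in positive tests.
- Section I, item 11 (Plan for Reporting Adverse Events) lists urine collection among the follow-up activities in the tracking system. It gives no schedule, which fits poorly with Section VI, item 3.

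**The concern.** A positive result can be recorded only for someone who was tested, and the chance of being tested depends on being in treatment. Engagement in treatment is the second primary outcome and is what the recovery coach and paramedic team sets out to raise. If a person with no test sits in the same cell as a person tested and negative, a cohort with more testing shows more positives at the same level of use. The frequency version is exposed too, because positives accumulate with the number of tests. The secondary aim acknowledges selective testing, but no step of the analysis uses that acknowledgement.

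At stake is the meaning of a significant chi-square result. It could reflect testing intensity and be read as an effect on opioid use, in either direction.

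**Working it through.** The plan states no expected value, testing rate or denominator for this outcome, so there is no figure of its own to reproduce. **Every rate below is an assumption**, chosen to show the mechanism and its range.

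**1. One test result per person.** Let u be the share using opioids (equal in all cohorts), t the share in treatment, and sT and sU the chance that a treated or untreated user has a recorded test. With the whole cohort as denominator:

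observed % = u × [t × sT + (1 − t) × sU]

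The gap between two cohorts is u × (t2 − t1) × (sT − sU). Take sT = 90% and t = 30% vs 60%.

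| u | sU | t = 30% | t = 60% | gap (points) |
|---|---|---|---|---|
| 40% | 10% | 13.6% | 23.2% | +9.6 |
| 40% | 30% | 19.2% | 26.4% | +7.2 |
| 40% | 50% | 24.8% | 29.6% | +4.8 |
| 60% | 10% | 20.4% | 34.8% | +14.4 |
| 60% | 30% | 28.8% | 39.6% | +10.8 |
| 60% | 50% | 37.2% | 44.4% | +7.2 |

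The gap is zero at sU = 90% and slightly negative (−1.2 and −1.8 points) at sU = 100%. For sU of 10% to 30%, a two-group test with an assumed 100 per group would be significant 23% to 63% of the time, against a nominal 5%.

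**2. Repeated tests over 180 days.** Suppose 45% vs 22% are engaged, engaged people have 6 tests, the rest have a 20% chance of one test, and each test is positive with probability 30% for everyone.

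- Share tested: 0.45 + 0.55 × 0.2 = 56% vs 0.22 + 0.78 × 0.2 = 38%.
- Any positive, independent tests: 0.45 × (1 − 0.7⁶) + 0.55 × 0.2 × 0.3 = 43.0% vs 0.22 × (1 − 0.7⁶) + 0.78 × 0.2 × 0.3 = 24.1%, a gap of 18.9 points.
- Any positive if use is a fixed trait, so that extra tests add nothing: 0.56 × 0.3 = 16.8% vs 0.376 × 0.3 = 11.3%, a gap of 5.5 points.
- Positive tests per person: 0.45 × 6 × 0.3 + 0.033 = 0.84 vs 0.22 × 6 × 0.3 + 0.047 = 0.44.

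With 100 per group, the two-group rejection rate is about 81% for independent tests and 21% for the fixed trait.

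**3. Against the BUP-started cohort.** Suppose 50% of the intervention cohort and 80% of the BUP cohort are in treatment, with sT = 90% and sU = 20%. At u = 40%: 0.4 × (0.45 + 0.10) = 22.0% vs 0.4 × (0.72 + 0.04) = 30.4%. At u = 60%: 33.0% vs 45.6%. The intervention cohort now looks better by 8.4 and 12.6 points at equal use.

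**4. The planned three-group test.** With t = 30%, 60% and 80% and sU = 20%, the 2-df test rejects 54% (u = 40%) to 80% (u = 60%) of the time with 100 per group, and 21% to 34% with about 100 people in total. The plan gives no comparator sizes.

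**5. Tested people only as denominator.** If untreated people are tested regardless of use, this removes the bias: 40% vs 40%. If untreated users are tested 50% of the time and untreated non-users 5%, then at u = 40% and t = 30% vs 60%:

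- t = 30%: 0.248 / 0.431 = 57.5%
- t = 60%: 0.296 / 0.632 = 46.8%

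The distortion runs the other way, so this denominator is not a sufficient cure.

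**6. When engagement truly lowers use.** Take 30% use if engaged and 60% if not, with the engagement shares of step 2. True use is 46.5% vs 53.4%. On the fixed-trait version with 20% of non-engaged people tested, the outcome shows 0.135 + 0.066 = 20.1% vs 0.066 + 0.094 = 16.0%, which reverses the sign. If 50% of non-engaged users are tested, it shows 0.135 + 0.165 = 30.0% vs 0.066 + 0.234 = 30.0%, and the reversal is gone.

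**The case against.** The strongest objection is that the documents nowhere state a whole-cohort denominator. The definition of X could mean a share of tests or of tested people, and the secondary aim speaks of the frequency of positive tests. This stands in part: counting the untested as No X is an inference from a percentage of individuals set in an X, No X, Total table. It is the natural reading. If it is not the intended one, the denominator is undefined and the plan still needs the rule.

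A reader might go further and infer that a cohort moved into treatment must look worse. The documents do not support that. The only concurrent comparator started BUP in the ED, whereas the intervention cohort refused it if offered (item 7), so the bias may flatter the intervention. How historical controls were tested is not described. The statement in item 3 that fewer than half of BUP starters stay engaged, roughly double the proportion after referral, describes the two comparator types. No engagement figure is given for the intervention cohort.

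A reader might also take testing to be essentially confined to people in treatment. The secondary aim names a second tested group, ED returners with opioid-related complaints, whose tests are plausibly triggered by use. That group shrinks the gap and can cancel it.

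The largest gap needs six independent tests accumulated over 180 days, and the plan states no cumulative rule. Finally, this is one of two secondary outcomes, the selective testing is openly disclosed, and self-reported use does not require a urine test. These points limit the consequence. They do not supply the missing rule.

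**Conclusion.** The point holds as a defect of specification with a real risk of bias. Followed as written, the urine comparison cannot separate opioid use from the chance of being tested. At identical use, the scenarios above give false gaps of roughly 5 to 19 percentage points, which shrink or vanish if untreated users are often tested in the ED. The sign is set by which cohort is tested more: probably unfavourable to the intervention against a less-treated group, possibly favourable against the BUP-started cohort, and unknown against historical controls. The size rests entirely on assumed testing, engagement and use rates. What rests on the documents alone is the absence of a not-tested category, the routine-care source of the tests, and the acknowledged link between testing, treatment and ED return. This should be changed, in proportion to its place as a secondary outcome.

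**What to change.** In item 12:

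- Show three categories per cohort at days 30 and 180: tested positive, tested negative, not tested.
- Report the number tested and the tests per person by cohort, split into programme-monitoring tests and ED or other clinical tests.
- Express frequency as positive tests divided by tests done.
- Give the percentage of individuals with two bounds, counting all untested people as negative and then all as positive.
- Present the tested-only percentage as descriptive and not as the main estimate, because ED-triggered tests are selected on use.
- State that a cohort difference is not read as an effect on opioid use where the bounds cross.
- Reconcile the mention of urine collection in item 11 with Section VI, item 3.

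The cost is wording and one extra count from charts already under review. The bounds will be wide. In the fixed-trait case of step 2 they are 16.8% to 60.8% (16.8 + 44.0 untested) vs 11.3% to 73.7% (11.3 + 62.4 untested), so they cross. This outcome will often stay descriptive, which is all that routine-care testing of this kind can support.

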Consent may be obtained at the ED, during community outreach events, electronically in a Yale School of Medicine version of REDCap®, or remotely (e.g., via email or picture), in accordance with University guidelines issued on 05/21/2020 from the Yale Center for Clinical Investigation. After consent and study initiation, either at the hospital or at some other time, the RCP team will perform a BNI—whose goal is to employ motivational techniques to help those with substance abuse consider their reasons for wanting to address dependency. Electronically, the RCP team will perform psychosocial and medical evaluations. (Please see the document, *Survey Tool and Handbook*, for details. It is included in our submission materials.) The RCP team will enter all data into a secured, encrypted database, REDCap®. To obtain consent or approximately 30 days after consent, the RCP team will schedule an electronic/remote (including by phone) Meeting 1 with participants. During this time, by remote interventions, the RCP team will collect and enter data into REDCap® based on discussions with and evaluations of participants. During an electronic/remote (including by phone) Meeting 2, which should occur no more than 180 days after consent, the RCP team will also collect and enter data into REDCap® based on discussions with and evaluations of participants. The study team will also enter data from participants' medical records at all time intervals. It is important to underscore that, due to the coronavirus pandemic, electronic and remote (including by phone) modalities will be utilized to the greatest extent possible.

Data from the entire cohort will be compared in aggregate with patients who were started on BUP in the ED over the same time period and with historic controls.¹¹

Figure 1. Screening + Enrollment

Genetic Testing N/A

A. Describe

- i. the types of future research to be conducted using the materials, specifying if immortalization of cell lines, whole exome or genome sequencing, genome wide association studies, or animal studies are planned *Write here*
 - ii. the plan for the collection of material or the conditions under which material will be received *Write here*
 - iii. the types of information about the donor/individual contributors that will be entered into a database *Write here*
 - iv. the methods to uphold confidentiality *Write here*

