3. Screen positive for OUD using mini international neuropsychiatric interview (MINI) (if applicable)	+	-
4. At least 1 opioid overdose requiring resuscitation by naloxone	+	-
5. Have a non-opioid overdose explanation for decreased level of consciousness, miosis, or decreased respiratory rate (if applicable)	-	+
6. Positive for OUD using a health questionnaire containing questions about prescription opioid and heroin use	+	-
7. Not in a critically ill state at the time of consent (e.g., not actively suicidal, psychotic, septic, and/or experiencing cardiac arrest)	+	-
8. 3.,4., & 6. (in this column) must have occurred within ≤ 7 days (inclusive) from date of consent if the prospective participant were immediately discharged from the emergency department (ED), floor, or other health care facility; consent may be obtained at any of these locations	+	-
9. Homicidal	-	+
10. Able to consent to program/study participation	+	-
11. Permanent residence is a long-term care/skilled nursing facility	-	+
12. Simultaneously enrolled in another study whose principal investigator (PI) or co-PI is a faculty member in the Department of Emergency Medicine	-	+
13. Prescribed opioids for acute pain, chronic pain, or palliative care without OUD	-	+
14. Stably enrolled in opioid agonist treatment or other medication-assisted therapy for OUD at the time of consent	-	+
15. In police custody or incarcerated (at the time of consent to participate or any known time after). (Parolees & those on probation may be eligible, but are NOT the target population and may be enrolled only incidentally .)	-	+
16. Refused buprenorphine/naloxone (BUP), if offered	+	-
17. Has a mailing address or P.O. box	+	-
18. Able to answer questions electronically/remotely (including by phone)	+	-

8. How will **eligibility** be determined, and by whom? *Write here*

In general, eligibility will be determined by the RCP team. ED and study staff may assist occasionally.

9. **Risks:** Describe the reasonably foreseeable risks, including risks to subject privacy, discomforts, or inconveniences associated with subjects participating in the research.

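### The plan compares self-reported opioid use and treatment engagement or remission with an ED-started BUP cohort for which it describes no interview, recovery capital score or day zero

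*Combined protocol and SAP*

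**What the plan says.** Item 12 (Statistical Considerations) has two primary outcomes: repeat overdose, and engagement in any treatment for opioid use disorder or remission. The second secondary outcome is "frequency and percentage of subjects with self-reported opioid use". On timing it says "Data will be recorded at baseline and at 30 and 180 days after consent to participate in the research".

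The analysis is one table with three rows: the RCP intervention, BUP initiated in the ED after overdose, and historical control(s). Chi-square "tests (2 df) will be employed to detect statistically significant differences". The table note applies the same outcomes to every row, including treatment engagement and, for the secondary outcomes, "or % (self-reported) opioid abuse".

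On sources, the secondary aim says "data will be collected remotely/electronically from self-report and EPIC". The principal aim also uses self-report and EPIC (the hospital record), with EPIC prevailing where they conflict. Remission is defined there as daily medication-assisted therapy and/or a recovery capital score of at least 27.5. Item 4 (Research Plan) names the BARC-10 interview for recovery capital and describes the contacts: evaluations after consent, Meeting 1 at about 30 days and Meeting 2 by 180 days, plus medical-record entry at all intervals.

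On the concurrent comparator, item 4 says only that the cohort's data "will be compared in aggregate with patients who were started on BUP in the ED over the same time period" and with historic controls. Inclusion criterion 16 (item 7) reads "Refused buprenorphine/naloxone (BUP), if offered".

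**The concern.** A three-row comparison needs each outcome to be obtainable in each row, by similar means and over similar time. For the ED-started BUP row the plan describes neither a way of asking about opioid use nor a date that starts the clock. If that cell were filled from incidental chart remarks, the test would set answers to a direct question against whatever a clinician happened to write down.

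The larger stake is primary outcome 2. Treatment outside the hospital system can be reported by an RCP participant at interview, while in an ED-BUP patient it counts only if it reaches EPIC. The recovery capital route to remission is open only to people who are interviewed. Both asymmetries add successes to the RCP row without any true difference, and a larger sample would not remove them.

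**Working it through.** **Step 1: who is interviewed.** Item 4 attaches every contact to consented participants. Four places put ED-started BUP patients outside that group:
- criterion 16 requires that BUP was refused if it was offered;
- the sample size paragraph in item 12 contrasts people expected to choose BUP in the ED with others expected to enrol;
- Section VI, item 1 lists ED-started BUP among the alternatives outside the research;
- Section III, item 1 gives a target of 100 participants in total, with no separate enrolment of a BUP cohort.

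**Step 2: what each concurrent row can contain, from the available text.**

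| Element | RCP | ED-started BUP |
|---|---|---|
| Self-reported opioid use | Interview, with EPIC prevailing in conflicts | No source described |
| Treatment engagement | Self-report plus EPIC | No source stated; EPIC most plausible |
| Recovery capital score | BARC-10 interview | No source described |
| Day zero for 30 and 180 days | Date of consent | None: no consent described |

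**Step 3: effect on the planned test.** Three cohorts by two outcome states give (3 − 1) × (2 − 1) = 2 degrees of freedom. With the ED-BUP row empty, that test cannot be run for self-reported use. What remains is RCP against the historical control, with (2 − 1) × (2 − 1) = 1 degree of freedom.

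**Step 4: illustration for engagement.** The plan gives no expected engagement rate by cohort and no figure for chart capture, so there is no planned number to reproduce. The sample size of about 100 is not an input to the argument. The following are assumptions:
- true engagement p is the same in both cohorts;
- capture is complete in RCP;
- a share s of true engagement is visible in EPIC for ED-BUP;
- n = 100 per cohort (the plan does not state the size of the ED-BUP cohort).

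The observed rates are p and p × s, so the false difference is p × (1 − s). The chance of a significant result favouring RCP, at two-sided 5%, is

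Φ{ [p₁ − p₂ − 1.96 √(2 p̄(1 − p̄)/n)] / √([p₁(1 − p₁) + p₂(1 − p₂)]/n) },

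with p₁ = p, p₂ = p × s and p̄ their mean. With no true difference this should be 2.5%.

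For p = 40%:

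| Chart capture s | Observed RCP | Observed ED-BUP | False difference | Chance of significance favouring RCP |
|---|---|---|---|---|
| 95% | 40% | 38% | 2 points | 5% |
| 90% | 40% | 36% | 4 points | 8% |
| 80% | 40% | 32% | 8 points | 22% |
| 70% | 40% | 28% | 12 points | 43% |
| 60% | 40% | 24% | 16 points | 68% |

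At s = 60%: p̄ = 0.32, and 1.96 × √(2 × 0.32 × 0.68/100) = 0.129. The denominator is √((0.24 + 0.1824)/100) = 0.065. Then (0.16 − 0.129)/0.065 is about 0.47, and Φ(0.47) is about 68%.

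Over the same range of s, p = 30% gives false differences of 1.5 to 12 points and a chance of 4% to 51%. For p = 60% they are 3 to 24 points and 6% to 93%.

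**The case against.** The strongest reply is that this argues from silence. No section says that the ED-BUP cohort is never contacted. Figures 1 and 2 are not shown in the available text, the Survey Tool and Handbook is not included, and the monitoring plan in item 11 mentions a monthly review of patients receiving BUP. This stands to the extent that a reader should not infer that the cohort has no contact at any time point; the text supports only that none is described. The monthly review does not say which patients it covers and is not outcome collection.

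Three other strong readings are tempting, and the documents do not support them:
- **Self-reported use has no comparator at all.** The historical control is a second comparator, and item 3 cites its source trial, with one other reference, for self-reported use. The gap is in one row. Whether that trial reports 180-day figures cannot be told from these documents.
- **RCP engagement is measured by interview alone.** EPIC is also used, and it prevails in conflicts. This narrows the asymmetry without closing it: outside care that is simply absent from EPIC is not clearly a conflict.
- **The bias is known to be large.** Chart capture of 50–70% would give 40% − 28% = 12 to 40% − 20% = 20 points, but that range leaves out high capture, and at 95% the bias is 2 points. Item 12 also expects some loss to follow-up, which would lower what RCP interviews pick up.

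A last objection concerns the remedy. RCP teams link people to methadone, intensive outpatient and residential programmes, which EPIC may miss, whereas item 3 describes ED-BUP patients as referred to a primary care clinic. An EPIC-only comparison could therefore undercount RCP more. This stands, and it limits how that comparison may be read.

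**Conclusion.** The concern holds for the concurrent cohort. As written, the plan compares self-reported opioid use with an ED-started BUP row that has no described source. It also compares a primary outcome that would be ascertained more fully in RCP than in ED-BUP, over windows that have no starting date in ED-BUP. That is more than a missing detail, because followed literally the analysis either cannot be run or sets unlike measurements against each other.

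The direction on primary outcome 2 can favour RCP. The size is unknown. The 2–16 points assume 40% true engagement in both cohorts, complete capture in RCP and 60–95% chart capture in ED-BUP. The significance probabilities also assume 100 per cohort. None of these inputs is in the documents. That EPIC would be the only ED-BUP source is the most plausible reading, not a stated fact.

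**What to change.** Amend item 12 as follows.

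1. **Self-reported use.** Remove the ED-BUP row from this comparison. Report within-person change in RCP from baseline to 30 and 180 days. Keep the historical comparison only at the time points and under the definitions that the cited trial reports.
2. **Primary outcome 2, RCP versus ED-BUP.** Compare treatment engagement abstracted from EPIC with the same form in both cohorts, over windows counted from the index overdose. Leave the recovery capital route to remission out of this between-cohort comparison.
3. **Fuller RCP result.** Report interview-plus-EPIC engagement or remission for RCP alongside. Do not claim an RCP advantage over ED-BUP that appears only when interview data are added.

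The cost is revised wording and one shared abstraction form. The plan gives up a between-cohort claim on self-reported use that it could not support. EPIC-only engagement will miss out-of-system care, possibly more in RCP, so the plan should state that limit and should not read a null EPIC-only result as evidence of no benefit.
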